1 LIST OF ACRONYMS

AE	Adverse Event
A1C	Hemoglobin A1c
AUC	Area Under the Curve
BMI	Body Mass Index
BG	Blood Glucose
CFR	Code of Federal Regulations
CGM	Continuous Glucose Monitor
CONSORT	Consolidated Standards of Reporting Trials
CRF	Case Report Form
CU	University of Colorado
FDA	Food and Drug Administration
GCP	Good Clinical Practice
GEM	Glycemic Excursion Minimization
HIPAA	Health Insurance Portability and Accountability Act
HSR	Health Sciences Research
ICH	International Conference on Harmonisation
IRB	Institutional Review Board
MRN	Medical Record Number
NCT	National Clinical Trial
PI	Principal Investigator

PPG	Postprandial Glucose
SAE	Serious Adverse Event
SMBG	Self Monitoring Blood Glucose
SOA	Schedule of Activities
SOC	Standard of Care
T2D	Type 2 Diabetes

2 PROTOCOL SUMMARY

Title	Libre 2 CGM plus glycemic excursion mIniMization (GEM) in the treatment of PrEDiabEtes: The IMPEDE Study
Funding Organization	Abbott
Site	University of Colorado
Study Design	2 between (groups) x 2 within (pre-post) partial cross-over randomized clinical trial
Study Description	
For people with prediabetes, it may be possible to delay or prevent the progression to diabetes by reducing postprandial glucose (PPG). Our Glycemic Excursion Minimization (GEM) lifestyle intervention guide can reduce PPG in people with type 2 diabetes and has been studied in this population with continuous glucose monitor (CGM) feedback to help the user learn what elevates and lowers their PPG. This study examines if the GEM lifestyle intervention guide plus continuous feedback from the Libre 2 CGM will allow participants with prediabetes with A1c 6.0-6.4 to (1) improve their metabolic status by illustrating the effects of their routine food and physical activity choices on their glucose levels and variability, more than Routine Care (RC), and (2) to enhance these investigations by adding comprehensive plasma proteomics to the analyses. We will recruit up to 70 adult participants with prediabetes through the University of Colorado, with the goal of having at least 30 participants complete the study. Participants will be randomized to the intervention or RC. Those randomized to the intervention will be given a GEM treatment manual, Libre2 CGM, and an activity monitor and will follow the GEM lifestyle intervention guide for 4 months. Those participants randomized to RC will follow recommendations from their primary care provider. RC participants will have the opportunity to receive GEM four months after consenting and completing the RC pre-post assessments. It is anticipated that 50% of the RC participants will want/be able to cross over to GEM upon completion of RC. Pre-post blinded CGM data and activity data, clinical, and psychosocial outcomes will be collected and analyzed. We anticipate this pilot project will demonstrate the benefits of using GEM plus Libre 2 to reduce percentage of CGM readings >120, from blinded pre-post LibrePro, as well as reduce BMI and depressive symptoms and increase modified diabetes empowerment. Comprehensive proteomics will be measured on small samples of EDTA treated venous blood. Individual proteins and protein pathways will be measured for each of the participants.

Primary Objective	To determine if individuals with prediabetes can use GEM plus Libre CGM to improve metabolic control.

Primary Endpoints	Pre-post reduction in percentage of CGM readings > 120 from blinded pre-post LibrePro; additional outcomes of particular interest include, A1C and BG variability
Secondary Objectives	
 (1) To determine if individuals with prediabetes can use the GEM manual with Libre CGM to improve other clinical, psychosocial, and behavioral outcomes. (2) To explore psychological (readiness to change) and physiological (proteomics) measures. (3) To generate user feedback about improving the intervention.
Secondary Endpoints	
 (1) Endpoints will include psychosocial scales, basic demographic information, comparative labs, Steps, Hours Active, or Active Minutes. (2) Analysis of individual proteins and protein pathways measured through use of a multiplex proteomics platform. (3) Endpoint will include the Program Importance Questionnaire
Participation Criteria	
Inclusion Criteria:
 
 • Age 25-70 years • A1C 6.0-6.4 • Documented diagnosis of prediabetes • Have a smart phone • Able to read English, as the GEM guide is currently only available in English • Willing and able to follow the study procedures as instructed 
Exclusion Criteria:
 
 • Diagnosis of diabetes mellitus • Currently taking any diabetes medication • Currently taking medication that promotes insulin resistance or otherwise interferes with metabolic control (e.g. prednisone) • Has a condition that precludes a low carbohydrate diet, such as gastroparesis • Has a physical or medical condition that precludes walking 120 steps per minute, for 10 minutes or longer • Has documented kidney disease that would preclude participation in study per PI discretion • Active or planned cancer treatment. • Extreme visual or hearing impairment that would impair ability to use real-time CGM • Pregnant or anticipates becoming pregnant in the next 4 months. • Anticipates moving within the next 4 months. • Treating physician, for any reason, considers their patient inappropriate for the study (e.g. uncontrolled bipolar disease)
Sample Size	Up to 70 screened participants with prediabetes and an A1c between 6.0-6.4 to provide a cohort of 36 enrolling in the trial, with a goal of at least 30 participants completing the trial.
Description of Study Intervention	Blinded CGM data (obtained through the use of the Libre Pro) and blinded activity data (obtained through the use of a FitBit) will be obtained for 2 weeks on all participants at the start and end of the study, and baseline clinical data collection and psychosocial scales will be completed prior to randomization. The intervention group will be given Libre 2 supplies for 4 months, an activity monitor, and the 4-chapter GEM paper guide. The intervention group will complete a virtual or inperson study visit where they will receive instructions on how to apply their unblinded Freestyle Libre and connect it to the study account, as well as how to

	
register their Fitbit to the study account. If the visit will be conducted remotely, participants will be mailed their CGM, Fitbit, and the GEM manual. Participants will receive one telephone call to review use of the GEM Guide and call at two weeks and six weeks later when the probability of dropouts from lifestyle intervention peaks. Participants will follow the self-directed GEM guide for 4 months (a 1-month treatment period followed by a 3-month maintenance period) while wearing a FitBit activity monitor and a Freestyle Libre 2 CGM. Participants will be given this guide and a study email so they can easily ask questions about the GEM program during treatment. Fielding GEM questions will help the study progress smoothly and will gain information that might improve the Guide in the future. Relevant questions and corresponding answers will be posted on a study website for all participants to review, if desired. However, all medical management questions will be referred back to the participant's treating physician. The GEM Guide for Prediabetes contains the following information in four chapters: Glucose Impact of Routine Choices, Recovering from BG Excursions, Reducing BG Excursions, and Maintenance. The RC group will follow recommendations from their primary care physicians and clinicians that will be tracked for later analysis. RC participants will have the opportunity to receive the intervention four months after consenting and completing of the RC pre-post assessments. Comprehensive proteomics analysis will be done at the same time after all samples have been collected.

Study Duration	
This study will last approximately 24 months from the beginning of subject recruitment to data analysis.

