5 STUDY DESIGN

5.1 Study Overview

This is a single center, 2 between (groups) x 2 within (pre-post) partial cross-over randomized clinical trial. A total of up to 70 subjects will be enrolled to allow for screen failures and up to 20% anticipated attrition, with the goal of ending the study with 20 subjects completing the GEM intervention, including those who crossover from the routine care arm for a total of 30 subjects completed an arm and/or both arms. Subjects who meet all inclusion criteria and none of the exclusion criteria will be entered into the study after informed consent.

Participants will be randomized to RC or GEM (2:1) where RC participants will have the opportunity to receive GEM four months after consenting and completion of the RC pre-post assessments. It was anticipated that 50% of the RC participants would want to and be able to cross over to GEM upon completion of RC.

However, 50% of our RC participants at post assessment did not qualify to cross over due to A1c being outside the 6.0-6.4 inclusion criteria range. This left less than 50% available to cross over to GEM, far fewer than anticipated. Given this reduced sample we will go from a 2:1 to a 1:1 randomization to RC. This allows allocating more participants directly assigned to GEM, thus relying less on RC crossovers. Given that this is a feasibility study and there were fewer participants that could cross over from RC to GEM due to post Routine Care A1c, the decision was made to change the randomization to 1:1. The investigator team felt this change was necessary in order to ensure that adequate data was collected from this feasibility study to power a larger study.

There will be 2 groups:

- Group 1. Routine Care (RC) participants will follow recommendations from their primary care providers. These recommendations will be tracked for later analyses.

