6.2 Number of Participants

A total of up to 70 participants, with 20-24 anticipated to complete GEM due to trial design anticipating 50% of RC participants will want/be able to cross over to the intervention group and eligibility criteria.

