10.4.3 Replacement of Subjects

Subjects who withdraw from the study will not be replaced.

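### The 20-24 GEM completers in Section 6.2 rest on a 50% crossover rate that Section 5.1 reports was not met, and 36 enrolled leaves no margin at the 20% attrition ceiling

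*Combined protocol and SAP*

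**What the plan says.** - **Section 2, Sample Size:** up to 70 are screened "to provide a cohort of 36 enrolling in the trial, with a goal of at least 30 participants completing the trial".
- **Section 2, Study Description:** half of the RC participants are expected, in the present tense, to cross over to GEM.
- **Section 5.1, recruitment:** "A total of up to 70 subjects will be enrolled to allow for screen failures and up to 20% anticipated attrition". The aim is 20 GEM completers, counting crossovers, among 30 completers in all.
- **Section 5.1, change of allocation:** RC to GEM was 2:1. Half of the RC participants then failed the A1c range at their post assessment. "This left less than 50% available to cross over to GEM, far fewer than anticipated". Allocation therefore becomes 1:1, so that the trial depends less on crossovers.
- **Section 5.1, last paragraph:** there is no formal power analysis. The main reason given for the size is that 20 participants completing the GEM path will allow an effect size to be estimated for a later application.
- **Section 6.2:** "20-24 anticipated to complete GEM due to trial design anticipating 50% of RC participants will want/be able to cross over".
- **Section 7.1.1:** allocation is still given as 2:1.
- **Section 10.4.3:** "Subjects who withdraw from the study will not be replaced".

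**The concern.** The current text uses a 50% crossover rate in two places and reports its failure in a third. Twenty GEM completers is the figure that carries the sample-size rationale. Section 6.2 supports it, and a top end of 24, with a rate that no longer applies. A reader cannot tell how many GEM completers the amended design should produce, or from what inputs.

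Two smaller problems make this worse. The enrolled cohort of 36 reaches the goal of 30 only if attrition stays below the ceiling that the plan allows. In addition, 70 is a screening number in Section 2 and an enrolment number in Section 5.1, so the denominator is unclear.

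**Working it through.** **Inputs from the documents.** 36 enrolled and a goal of 30 completers (Section 2); attrition up to 20%, a goal of 20 GEM completers, allocation changed from 2:1 to 1:1, and crossover availability below 50% (Section 5.1); 20-24 GEM completers at 50% crossover (Section 6.2); no replacement (Section 10.4.3).

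**Not given.** The exact crossover rate *c*, the number already randomised 2:1, and attrition by period. Where needed, I assume that 12 to 24 of the 36 were already allocated 2:1 and that both arms lose the same proportion in period 1.

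**1. Reproducing 20-24.** GEM completers = G + c × R, where G is the number randomised to GEM and R the number randomised to RC who complete period 1.
- 30 completers at 2:1, c = 50%: 10 + 0.5 × 20 = 20.
- 36 at 2:1 with no attrition, c = 50%: 12 + 0.5 × 24 = 24.

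Both ends reproduce exactly from the original plan, but the upper end needs zero attrition. At 1:1 and the same 50%, the two sums would be 15 + 7.5 = 22.5 and 18 + 9 = 27, so the range was not updated with the allocation.

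**2. Crossover needed now, with 30 completers and no loss after crossover.** Required c = (target − G)/R.

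| Allocation of the 36 | G | R | c for 20 | c for 24 |
|---|---|---|---|---|
| All 1:1 | 15.0 | 15.0 | 33% | 60% |
| 12 at 2:1, 24 at 1:1 (16 GEM, 20 RC) | 13.3 | 16.7 | 40% | 64% |
| 24 at 2:1, 12 at 1:1 (14 GEM, 22 RC) | 11.7 | 18.3 | 45% | 67% |
| All 2:1 | 10.0 | 20.0 | 50% | 70% |

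The first row is a bound, because Section 5.1 describes RC participants who had already finished under 2:1. In every row, 24 needs more than the reported ceiling of just under 50%. In the first three rows, 20 needs less than 50%.

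**3. 36 enrolled at the attrition ceiling.**
- 36 × 0.80 = 28.8 completers.
- Reaching 30 requires attrition of at most 1 − 30/36 = 16.7%.
- If each participant completes with probability 0.80, the binomial probability of at least 30 of 36 is 0.40.

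**4. GEM completers at 20% period-1 attrition.** With 12 already at 2:1, G = 0.8 × 16 = 12.8 and R = 0.8 × 20 = 16.0. With 24 already at 2:1, G = 0.8 × 14 = 11.2 and R = 0.8 × 22 = 17.6. The 25% crossover rate is an assumption, chosen to show sensitivity.

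| Loss after crossover | c | 12 at 2:1 | 24 at 2:1 |
|---|---|---|---|
| None | 50% | 12.8 + 8.0 = 20.8 | 11.2 + 8.8 = 20.0 |
| None | 25% | 12.8 + 4.0 = 16.8 | 11.2 + 4.4 = 15.6 |
| 20% | 50% | 12.8 + 6.4 = 19.2 | 11.2 + 7.04 = 18.2 |
| 20% | 25% | 12.8 + 3.2 = 16.0 | 11.2 + 3.52 = 14.7 |

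**5. Effect on precision.** The 95% confidence half-width for a mean change, in SD units, is t/√n: 2.093/√20 = 0.47 at n = 20 and 2.131/√16 = 0.53 at n = 16.

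**The case against.** - **Ceiling and goal.** The 20% is a ceiling, 30 is a goal, and 30 of 36 is a 16.7% loss, inside the ceiling. A reader might infer that 36 to 30 is an arithmetic error. The documents do not support that. Section 5.1 also attaches the 20% to the 70, not explicitly to the 36. What stands is only that 36 has no margin at the ceiling.
- **The move to 1:1 answers the shortfall.** Section 5.1 reports the failed expectation in the past tense and changes the allocation to rely less on crossovers. This is a real mitigation, and it keeps 20 within reach. It does not repair Section 6.2, which still gives 50% crossover as its reason.
- **The same range can come from 1:1.** If all 36 were allocated 1:1 and one third crossed over, 30 completers would give 15 + 5 = 20, and 36 with no attrition would give 18 + 6 = 24. That is correct arithmetic. But the documents state no one-third rate, some participants were allocated 2:1, and the upper end again needs zero attrition. It does not rescue the stated basis.
- **Less than 50% may already include willingness.** Half failing on A1c leaves half eligible, so the lower availability may already reflect who agreed. A further discount for willingness could count it twice, and none is applied here.
- **The consequences are small.** This is a pilot with no precision target, and Section 5.1 cites an earlier study in which 15 participants sufficed for a pre-post effect. That is fair, and it limits the weight of the point.

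**Conclusion.** The point holds as a figure that the plan relies on but whose stated basis it contradicts. The 20-24 range belongs to the superseded plan of 2:1 allocation and 50% crossover. With 30 completers and no loss after crossover, 24 is out of reach at any rate below 50%: it needs 60% if all were 1:1, or 64% to 67% if 12 to 24 were already allocated 2:1. Twenty needs 33% to 45% and is possible but not assured. Separately, 36 enrolled gives 28.8 completers at the attrition ceiling.

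A reader might go further and infer that the design cannot deliver 20 GEM completers, or that about 15-19 is what the observed crossover rate implies. Neither is supported. The documents give no observed rate beyond its being below 50%, no count already allocated 2:1, and no attrition by period. The 15-19 range (14.7 to 19.2) appears only with assumed crossover of 25% to 50%, 12 to 24 already at 2:1, and 20% loss in each period; without loss after crossover it becomes 15.6 to 20.8. Even at 16 completers, the loss of precision against 20 is modest (0.53 against 0.47 SD). The matter should be corrected, but it does not threaten the pilot.

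**What to change.** - **Sections 5.1 and 6.2:** restate the GEM completer figure from the actual numbers randomised under each ratio, the site's observed crossover count and the stated attrition, with these inputs beside it. Any range such as 15-19 should appear only as conditional on listed assumptions, not as an observed-rate figure.
- **Sections 2 and 6.2:** replace the 50% crossover statements.
- **Section 2, Sample Size:** state about 29 completers at 20% attrition, or state that 30 assumes attrition of at most 16.7%.
- **Throughout:** use 70 as the screening cap and 36 as the number randomised.
- **Section 7.1.1:** replace 2:1 with the allocation history given in Section 5.1.

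The site should hold the counts needed, so the cost is wording. No added enrolment is required, and the stated figures may become slightly less favourable.

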4.1 Primary Objective

The primary outcome variable will be participants' pre-post reduction in percentage of CGM readings >120, from blinded pre-post LibrePro. This is most relevant since the goal of GEM is to reduce glucose excursions and since 13% of non-diabetic adults' CGM readings exceed 120.²³

Our hypothesis is that participants assigned to the intervention group will achieve a greater pre-post reduction in percentage of CGM readings >120 than will the control group.

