- Group 2. GEM participants will be given Libre 2 supplies for 4.5 months, an activity monitor and the 4-chapter paper GEM guide which provides: 1) decisive didactic information about the effects of net carbohydrate consumption and routine physical activity on blood glucose fluctuations; 2) instructions to systematically use CGM feedback to educate them about how carbohydrates and physical activity impact their BG excursions, motivate them to repeat choices that lead to lower AUC, activate them to take steps to lower their BG elevations when detected by the high glucose alarm, and investigate the BG impact of new food and activity choices

concerning their effect on their BG; 3) employ structured self-monitoring (diary) to organize and identify personal patterns in their food and physical choices that impact their AUC; 4) GEM Supplement that provides additional information to the manual, e.g. frequently asked questions and answers, nutrient content of low glycemic load foods, case reports, youtube exercise videos; and 5) automated personalized daily text messages to “choose wisely” food and activity choices, and perform daily diary entries. The GEM manual for this prediabetes sample will follow the same format as that used with our diabetes sample: 1) become aware of metabolic costs of routine choices, 2) minimize BG elevations with personally relevant food choices, 3) hasten BG recovery with increased routine physical activity, and 4) plan for continuation of such lifestyle changes. The major adaptation in the GEM Guide for this prediabetes population focused on reducing risk of progression to diabetes and having to initiate diabetes medications. The GEM Guide was adapted based on clinical experience, the qualitative analyses of Yost et al,²⁰ and the literature on secondary prevention.³⁰

Given that this is a pilot study, we did not perform a formal power analysis at this time because there are no data suggesting anticipated change in AUC for adults with prediabetes. However, 20 participants completing the GEM path through the study will provide data to estimate this effect size and therefore to enable power analysis for an anticipated follow-up NIH application. Additionally, N=15 was sufficient to find a pre-post effect in a previous study evaluating a different intervention in a prediabetes population.²⁰

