8.3 Clinical Assessments

- CGM metrics including time >120 and GV
 - CGM will be fully blinded to the participant, unless on GEM so they may assess lifestyle modifications, and used to collect baseline and primary outcome data in a manner that will not bias RC subjects' activity as the CGM is programmed not to display values, only record values
- Height/Weight and BMI
- Blood pressure
- A1C
- Total cholesterol
- Triglycerides
- HDL
- LDL
- Presence of Atrial fibrillation
- Comprehensive proteomics

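### The study website with answers to GEM questions is not restricted to people who have started GEM, so Routine Care participants could read intervention content during their control period

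*Combined protocol and SAP*

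**What the plan says.** Section 2, Description of Study Intervention, gives participants following GEM a channel for questions: "Participants will be given this guide and a study email so they can easily ask questions about the GEM program during treatment". It then says of the answers: "Relevant questions and corresponding answers will be posted on a study website for all participants to review, if desired". This is the only mention of the question-and-answer site.

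Section 5.1 lists similar material among the components given to Group 2 (GEM): "GEM Supplement that provides additional information to the manual, e.g. frequently asked questions and answers".

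The control condition is described separately, after the website sentence: "The RC group will follow recommendations from their primary care physicians and clinicians that will be tracked for later analysis". Section 8.3 explains that the CGM is blinded so as to collect "primary outcome data in a manner that will not bias RC subjects" in their activity. The primary hypothesis in Section 4.1 is that "participants assigned to the intervention group will achieve a greater pre-post reduction in percentage of CGM readings >120 than will the control group".

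**The concern.** RC is meant to be whatever primary care recommends. Answers to questions about GEM are intervention material, and a page open to everyone enrolled would put some of it within reach of the control arm for the whole control period, about 4.5 months under Section 9.4.1.

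Two comparisons would be exposed:

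- **Period 1.** If RC participants act on what they read and lower their glucose readings, the difference from GEM narrows.
- **Period 2.** The sensor worn after RC End also supplies the starting value for those who cross over, so an exposed crossover would start GEM from an already lowered baseline.

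The protocol tracks primary care recommendations in RC but plans no record of website use. Exposure could therefore be neither detected nor described afterwards.

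**Working it through.** The plan states no figure on this point, so the check is mainly a comparison of passages.

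**1. Who is meant by all participants?** Section 2 supports two readings.

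- *Both arms:* the same description opens by saying that blinded CGM and activity data "will be obtained for 2 weeks on all participants at the start and end of the study". There the phrase plainly covers everyone.
- *GEM only:* just before the website sentence, the word means GEM recipients, as in "Participants will follow the self-directed GEM guide for 4 months" and in the sentence about the guide and study email. RC is introduced only afterwards.

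The local context favors GEM only. The literal wording includes RC. No other section settles it.

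**2. Is the content part of the intervention?** Section 5.1 places frequently asked questions and answers in the GEM Supplement, under Group 2. The documents do not say that the website and the Supplement are the same thing, but posted answers to GEM questions are the same kind of material.

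**3. Is there a barrier, or a route, for RC?** No log-in, arm restriction, instruction to RC participants or access record is described. Nor does RC Start (9.4.1) or RC End (9.5.1) point RC participants to the site. That silence is weak evidence, because the GEM visit steps (9.4.2, 9.6) do not mention the site either.

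**4. Which analyses would be touched?**

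- Section 11.3 compares the groups in study period 1, which is when RC exposure would occur.
- RC End (9.5.1, step 2) hands out the blinded sensor, Visit 4/5 (9.6, step 2) acquires the data, and Appendix 1 shows no new blinded sensor at Visit 4/5. The RC post window is therefore the crossover's GEM baseline for the period-2 paired test in Section 11.3.
- The pre-post change of participants randomized directly to GEM is unaffected.

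**5. Direction and size.** Let *d* be the true GEM-minus-RC difference in change, *c* the share of RC participants who use the site, and *r* the fraction of the GEM effect they gain from it. The observed contrast is

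*d* − *c·r·d* = *d*(1 − *c·r*).

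Neither *c* nor *r* is in the documents. Assumed values, for illustration only:

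| *c·r* | Contrast kept |
|---|---|
| 0 (access limited to GEM) | 100% |
| 0.05 (e.g. *c* = 0.2, *r* = 0.25) | 95% |
| 0.10 | 90% |
| 0.25 (e.g. *c* = 0.5, *r* = 0.5) | 75% |

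Section 3.2 says GEM presumes accurate and timely glucose feedback. RC participants have only blinded CGM, hand in the activity monitor at RC Start, and receive no guide, calls or texts. High values of *r* are therefore hard to support.

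**The case against.** The strongest reply is that the sentence was never meant to cover RC. From the point where the intervention group's visit is described, participants means people using GEM. If it meant both arms, RC would also receive the guide, which the rest of the protocol rules out. Section 5.1 treats such material as belonging to Group 2, and no RC visit step mentions a website. The consent text is not available, so what RC participants were told cannot be seen. Any bias would run toward no effect and could not create a false benefit. Section 5.1 also ties the planned effect-size estimate to participants completing GEM, and the change in those randomized directly to GEM cannot be altered by RC website use.

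Most of this stands, and it limits the point to a conditional one. A reader might infer that the posting does shrink the primary contrast, that it distorts the baseline of all crossovers, or that it inflates a later trial's sample size by a definite percentage. The documents support none of these. They show neither RC access nor its effect, only crossovers who had used the site would be affected, and any percentage would rest on chosen values of *c* and *r*.

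What the reply does not remove is the gap itself. Even on the narrow reading, nothing keeps RC participants out, and whoever builds the page has only this sentence to follow.

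**Conclusion.** The point holds as a conditional risk from an unrestricted instruction. Followed literally, the plan opens GEM content to RC participants during study period 1 and during the post window that serves as the crossover baseline. If RC participants use it and benefit, the between-group contrast and the period-2 change of exposed crossovers could be biased toward no effect. This rests on two unverified assumptions: that RC participants can and do reach the site, and that its text alone changes their glucose. The size is unknown and probably partial; if access is limited to GEM recipients, it is zero. This is an inexpensive improvement to the protocol, not a demonstrated flaw in the trial's results.

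**What to change.** In Section 2, replace the open-access wording with: *posted on an access-restricted page for participants who have started GEM*. Issue access at GEM Start (9.4.2). For crossovers, issue it at Visit 4/5 (9.6) and not at RC End, so that the RC post sensor wear is finished first.

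Section 5.1 shows that some RC participants have already reached post assessment, so a forward-looking edit is not enough. Establish whether RC participants have had access so far, record any use, and report it with the primary results.

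The cost is one sentence, a log-in and a short check of past access. GEM participants lose nothing, and crossovers receive the material when they start GEM. The change also extends to the website the intent behind blinding the CGM in Section 8.3.
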